3.2 Exclusion Criteria

Patients who meet any of these criteria are not eligible for enrollment as study participants

- Prematurity: < 37 weeks post gestational age at time of surgery
- Treatment with intravenous steroids within the two days prior to scheduled surgery.
- Participation in research studies involving the evaluation of investigational drugs or vaccines within 30 days of randomization.
- Suspected infection that would contraindicate steroid use (e.g. – Herpes)
- Known hypersensitivity to IVMP or one of its components or other contraindication to steroid therapy (e.g. - gastrointestinal bleeding).
- Preoperative use of mechanical circulatory support or active resuscitation at the time of proposed randomization.
- Inability to comply with study procedures.

4 Study Design

This is a multi-center, prospective, randomized, double blind, placebo controlled study of intraoperative MP in neonates undergoing CPB. Patients will be allocated to one of the 2 study groups in the ratio of 1:1. The randomization will be stratified by corrective vs. palliative surgery and by surgeon. The Primary Endpoint is a composite morbidity-mortality outcome, evaluated as intention to treat (ITT). Secondary endpoints include inotropic score, incidence of LCOS, fluid balance, ICU stay parameters, levels of inflammatory markers, safety parameters, and neurodevelopmental outcomes at 1 year. A two-sided test with a type I error rate of 0.05 will be used for all endpoints with no adjustments of the p-value for multiple testing.

It is expected that 190 patients (95 patients per treatment arm) will be needed to be enrolled in the study to show a significant difference between groups. The annual amount of eligible & consenting patients at MUSC for this trial and a similar trial over 3 years was 35 cases/year. The annual amount of eligible patients at Children's Healthcare of Atlanta based on the surgical volume in 2012 would be 74 neonates. Anticipating a 70% consent rate would result in 50 cases a year. As such, this study would expect to reach the goal of 190 evaluable subjects in 4 years, within the 5 year proposed grant cycle.

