7.1.3 Randomization

This is a randomized placebo-controlled multicenter study of intraoperative MP in neonates undergoing CPB. The goal for subject randomization for this trial is to prevent potential selection biases, prevent serious imbalances in the distributions of important baseline prognostic factors and ensure the compatibility of the two subject groups. Based on knowledge from previous studies and clinical experiences, cardiac operation (corrective vs. palliative surgery) and surgeon are potential prognostic factors that may affect the primary outcome. Serious imbalances in the distribution of either of these two factors may reduce the compatibility of the study groups, and therefore affect the interpretation and the recipient of the trial results. Eligible subjects are randomized at 1:1 ratio to either the intraoperative methylprednisolone (MP) or placebo treatment group. See section 11 for more details. Randomization should occur as close as possible to scheduled surgery but may occur at any time prior to surgery.

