11.1 Randomization

11.1.1 Randomization Code Development

The randomization scheme will be designed by the project biostatistician in collaboration with the investigational pharmacy. A permuted block randomization scheme stratified by cardiac operation and surgeon will be used so that imbalances between the two treatment group sizes within each stratum (cardiac operation by surgeon) will be contained. A list of randomization codes will be generated by the study statistician with information on stratum number, stratum name, a sequential ID, 4-digit subject randomization code in random order, treatment code (1 or 2), and treatment name (MP or placebo).

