12.3 Subgroup Analyses

The modified ITT population, defined as the set of all patients randomized to treatment and underwent cardiopulmonary bypass, will be analyzed and presented for the Primary Endpoint. The same analyses will be conducted on the PP population, defined as those patients who are randomized, receive study drug as defined in the protocol, and have no major protocol violations preventing analysis (e.g. – post-op patients who receive steroids off-protocol). A two-sided test

with alpha of 0.05 will be used. The following subgroups will be analyzed for the Primary Endpoint:

Underlying diagnosis:	Palliated vs. Corrective procedure
Age:	≤ 7 days vs. >7 days
Body weight:	≤ 2.5 kg vs. >2.5 kg

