12.4 Statistical Methods

Descriptive statistics will be used to characterize the two treatment groups with respect to demographics and baseline clinical characteristics. T-tests, chi-square tests, and non-parametric statistical tests will be used, as appropriate, to compare the groups at baseline. Any significant imbalances will be accounted for in the analyses using multivariable techniques. The primary intention-to-treat analysis comparing the composite outcome between treatment groups will be conducted using generalized linear model. The primary analysis will be adjusted for underlying diagnosis and surgeon. Logistic regression models will be used for the per-protocol analysis and for analyses of secondary categorical outcomes. For continuous variables such as change from baseline in vital signs, hematology, and clinical chemistry parameters, analysis of covariance (ANCOVA) will be utilized with the baseline value used as covariates. Unless otherwise stated, baseline is defined as the last observation before the administration of the study drug. Time to event data (duration of mechanical ventilation, length of ICU stay, and length of hospitalization) will be assessed via non-parametric log-rank tests.

Once half of the study subjects have been recruited and assessed, an interim analysis will also be conducted and presented to the DSMC, for which the p-value thresholds for stopping the study for superiority or futility will be 0.003 and 0.72, respectively. The p-value used at the end of the study with full enrollment will be 0.049, preserving an experiment-wise 2-sided alpha level of 0.05. These stopping thresholds are based on an O'Brien-Fleming alpha spending function. All analyses will be conducted in SAS v9.2 (Cary, NC).

Multiple correlation analyses will be performed between the inflammatory markers and other continuous outcome measures, such as fluid balance, inotropic score and hemodynamic variables. An assessment will also be made of the association between the inflammatory markers and categorical variables, such as the composite morbidity-mortality outcome and its components. Analyzed safety variables will include all reported adverse events, the incidence of acute renal injury and postoperative creatinine, hyperglycemia and infection. All patients who are randomized, received study drug, and underwent cardiopulmonary bypass will be included in the safety analyses.

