12.10 Statistical Methods

Descriptive statistics will be used to characterize the two treatment groups with respect to demographics and baseline clinical characteristics. T-tests, chi-square tests, and non-parametric statistical tests will be used, as appropriate, to compare the groups at baseline. Any significant imbalances will be accounted for in the analyses using multivariable techniques. The primary intention-to-treat analysis comparing the composite outcome between treatment groups will be conducted using generalized linear model. The primary analysis will be adjusted for underlying diagnosis and surgeon. Logistic regression models will be used for the per-protocol analysis and for analyses of secondary categorical outcomes. For continuous variables such as change from baseline in vital signs, hematology, and clinical chemistry parameters, analysis of covariance (ANCOVA) will be utilized with the baseline value used as covariates. Unless otherwise stated, baseline is defined as the last observation before the administration of the study drug. Time to event data (duration of mechanical ventilation, length of ICU stay, and length of hospitalization) will be assessed via non-parametric log-rank tests.

Once half of the study subjects have been recruited and assessed, an interim analysis will also be conducted and presented to the DSMB, for which the p-value thresholds for stopping the study for superiority or futility will be 0.003 and 0.72, respectively. The p-value used at the end of the study with full enrollment will be 0.049, preserving an experimentwise 2-sided alpha level of 0.05. These stopping thresholds are based on an O'Brien-Fleming alpha spending function. For an additional level of safety oversight, the PI will place enrollment on temporary hold if 1 year mortality exceeds 35.5% and the DSMB will be asked to provide an expedited data safety review, concluding with next step recommendations. All analyses will be conducted in SAS v9.2 (Cary, NC).

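### The secondary analyses do not name the randomisation strata; if the strata are prognostic, the tests are conservative and forgo some power

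*Combined protocol and SAP*

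**What the plan says.** **Randomisation.** Section 4 (Study Design) states: "The randomization will be stratified by corrective vs. palliative surgery and by surgeon". Section 11.1.1 gives the method: "A permuted block randomization scheme stratified by cardiac operation and surgeon will be used". Section 7.1.3 gives the reason, that "cardiac operation (corrective vs. palliative surgery) and surgeon are potential prognostic factors that may affect the primary outcome". Block size, number of surgeons and size of the stratum effects are not stated.

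**Primary analysis.** Section 12.4, repeated in 12.10, says: "The primary analysis will be adjusted for underlying diagnosis and surgeon. Logistic regression models will be used for the per-protocol analysis". The subgroup lists in 12.3 and 12.9 define underlying diagnosis as "Palliated vs. Corrective procedure", so both stratification factors are in the primary model.

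**Other analyses** (12.4 and 12.10):
- Categorical and per-protocol: "Logistic regression models will be used for the per-protocol analysis and for analyses of secondary categorical outcomes". No covariates are listed.
- Continuous change from baseline: ANCOVA, with baseline as the only named covariate.
- Durations: "Time to event data (duration of mechanical ventilation, length of ICU stay, and length of hospitalization) will be assessed via non-parametric log-rank tests". No stratification is mentioned.
- A general clause allows multivariable adjustment for baseline factors that turn out significantly imbalanced.

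Sections 12.3 and 12.9 also say that the per-protocol population receives the same analyses as the main population.

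**The concern.** Blocking within strata removes most of the between-stratum variation from the treatment comparison. An analysis that omits the strata still counts that variation in its standard error. If the strata predict the outcome, the standard error is too large, the interval too wide and the test too cautious. Precision that the randomisation has already secured goes unused.

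The imbalance clause is a poor substitute. Blocking keeps exactly these factors balanced, so a significance-triggered rule will rarely bring them in.

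What is at stake is efficiency and prespecification in the secondary aims. One of those, in section 2.2, expects similar adverse event rates in the two arms. A test running below its nominal level is somewhat less able to show a difference there.

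**Working it through.** **1. The plan's own secondary powers (12.2 and 12.8; two-sided 0.05).** Power = Phi(d/SE − 1.96), with SE = SD × sqrt(2/n).

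- Inotropic score: n = 95 per arm, d = 2, SDs 3.6 and 3.9 (average 3.75). SE = 3.75 × sqrt(2/95) = 0.544; 2/0.544 = 3.68; power 95.7%. The plan says above 95%: reproduced. (At SD 3.6 it is 96.9%, at 3.9 it is 94.2%.)
- Bayley: 95 × 0.85 = 80.75, about 81 per arm; d = 5, SD 7.25. SE = 1.139; 5/1.139 = 4.39; power 99.2%. The plan says 99%: reproduced.
- ICU stay: about 75%, from a simulation of a skewed distribution that is not given. It cannot be reproduced. A simple 20% versus 40% comparison gives 85.9%, but that is a different test.

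The first two use total SDs, so they describe unadjusted tests.

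**2. Effect of omitting the strata, continuous outcome.** With arms balanced within strata, the unadjusted z statistic has variance 1 − R2. Therefore:

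- true type I error = 2[1 − Phi(1.96/sqrt(1 − R2))]
- unadjusted power = Phi((d/SE − 1.96)/sqrt(1 − R2))
- adjusted power = Phi(d/(SE × sqrt(1 − R2)) − 1.96)

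Example at R2 = 0.2: sqrt(0.8) = 0.894; 1.96/0.894 = 2.19; type I error 2.8%. The interval is 1/0.894 = 1.12 times as wide as it need be.

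| Assumed R2 | Type I error, unadjusted | Inotropic d = 2: unadjusted / adjusted power | Inotropic d = 1.5: unadjusted / adjusted power |
|---|---|---|---|
| 0 | 5.0% | 95.7 / 95.7% | 78.7 / 78.7% |
| 0.05 | 4.4% | 96.1 / 96.5% | 79.3 / 80.7% |
| 0.10 | 3.9% | 96.5 / 97.2% | 80.0 / 82.8% |
| 0.20 | 2.8% | 97.3 / 98.4% | 81.4 / 86.9% |
| 0.30 | 1.9% | 98.0 / 99.3% | 83.0 / 90.9% |

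The difference of 1.5 is an assumption, chosen to put power near 80%. Bayley power at 5 points exceeds 99% with or without adjustment throughout.

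**3. Simulation across outcome types.** There were 4,000 trials per setting with 190 infants, blocks of 4, and 4 or 8 surgeons crossed with 2 operation types. Operation type was assumed to carry two thirds of the between-stratum variance. The adjusted tests used every operation-by-surgeon cell: a linear model, Mantel-Haenszel (standing in for logistic regression) and a stratified log-rank test. Scenarios were a continuous difference of 1.5, binary 40% versus 20%, and a log-rank shift of 0.44 SD. Results are for 4 surgeons; 8 surgeons gave similar values.

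| R2 | Type I error, unadjusted: continuous / binary / log-rank | Power, continuous: unadjusted → adjusted | Power, binary | Power, log-rank |
|---|---|---|---|---|
| 0.1 | 4.0 / 4.4 / 4.4% | 77.7 → 80.6% | 86.7 → 87.8% | 78.0 → 80.6% |
| 0.2 | 3.0 / 3.4 / 3.4% | 81.8 → 87.4% | 87.4 → 90.0% | 81.4 → 87.0% |
| 0.3 | 2.0 / 2.8 / 2.4% | 81.6 → 90.5% | 88.0 → 92.1% | 81.4 → 89.7% |

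Over R2 of 0.1 to 0.3 and both surgeon counts, the adjusted tests had type I error of 4.5% to 5.6%. That is nominal within simulation error: sqrt(0.05 × 0.95/4000) = 0.3 points.

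With 8 surgeons and R2 = 0, stratifying the log-rank test by all 16 cells cost about 2 points of power (79.0% to 77.2%). Thin strata therefore have a price.

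**The case against.** **The stated powers do not fall.** This is the strongest objection, and it stands. A reader might infer that the plan's 80%-type figures drop, because a test with 80% power when adjusted has about 73% when unadjusted at R2 = 0.2. That takes an adjusted design as the reference, and the reproducible secondary powers were not built that way. Against a nominal unadjusted 80%, where d/SE − 1.96 = 0.84, true unadjusted power at R2 = 0.2 is Phi(0.84/0.894), about 83%. The adjusted test reaches about 88%. The loss is unused efficiency.

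**ICU stay.** A reader might also infer that about 75% power leaves ICU stay especially exposed. The plan describes that simulation by the overall distribution and mentions no strata, so nothing shows that it presumed an adjusted test.

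**The text is less firm than 'ignores the strata'.** This stands in part. The logistic covariates are unlisted, which is under-specification and not a declared unadjusted model. The per-protocol sentence in 12.3 and 12.9 points to an adjusted analysis, in tension with the bare logistic model in 12.4 and 12.10. No test is named for Bayley or for days alive and out of hospital. Section 12.11 refers to a subsequent SAP that could carry covariate lists. Even so, the log-rank and ANCOVA specifications as written contain no stratum terms.

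**The strength of the strata is assumed.** This stands. Section 7.1.3 calls them potential factors, and only for the primary outcome. For the ANCOVA, the relevant R2 is what the strata explain beyond the baseline value, which may be smaller.

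**The error is conservative and confined to secondary and per-protocol analyses.** True. It limits the importance of the point but is no reason to leave the wording as it is.

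**Conclusion.** The point holds as one of efficiency and specification. The plan stratifies by two factors, carries them into the primary model, and does not name them for the secondary analyses.

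The direction is secure whenever the strata predict the outcome; the size is conditional on R2. Across 0.1 to 0.3, power forgone at the scenarios examined is about 3 to 9 points for continuous outcomes, 1 to 4 for binary and 2 to 8 for log-rank, and true type I error runs from about 4% down to 2% (nearer 3% for binary at the upper end). With R2 of 0.05 or less the omission hardly matters, and with no stratum effect it does not matter at all. At the plan's own inotropic and Bayley effects, power is so high that adjustment adds little.

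The documents do not support a claim of false-positive risk or of a shortfall against any stated power. The change is still worth making, because it needs only data already used to randomise and settles covariates before the data are seen.

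**What to change.** In sections 12.4 and 12.10, state that:

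- secondary ANCOVA and logistic models include operation type and surgeon, with low-volume surgeons pooled within site;
- where events are sparse, the logistic model includes operation type only, under a threshold set in advance;
- log-rank tests are stratified by operation type;
- the per-protocol logistic model uses the same covariates as the primary analysis, which reconciles it with 12.3 and 12.9.

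Stratifying the log-rank tests by operation type alone avoids thin cells. It recovers only the part of the gain due to operation type, so the simulated log-rank gains are an upper guide under those assumptions.

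The cost is SAP wording; both factors are known for every infant at randomisation. There are two small downsides. Adjusted odds ratios are conditional on the covariates and should be reported as such, and the rules for pooling surgeons and for sparse events must be written down before unblinding.

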1.3 Preclinical and Clinical Experience

1.3.1 Clinical Experience

Given the rationale of glucocorticoid administration in the setting of CPB is targeted at the reduction of the responsiveness of the immune system to the CPB stimuli, the preventive effect of glucocorticoids would be presumed to be augmented by administration prior to the inflammatory stimulus. Animal research⁴⁶ and small clinical observations²⁹ support this presumption. However, recent work by [name] (PI) challenged this canonical belief and provides the rationale for this investigation⁵. Neonates scheduled for cardiac surgery were randomly assigned to receive either Two Dose (8 hours preoperatively and operatively; n=39) or Single Dose (operatively; n=37) methylprednisolone (MP; 30 mg/kg/dose) in a prospective, double-blind, controlled trial. The primary outcome was the incidence of low cardiac output syndrome or death 36 hours postoperatively. Secondary outcomes were death at 30 days, interleukin-6 levels, inotropic score, fluid balance, serum creatinine, and ICU and hospital stay. Preoperative plasma levels of the inflammatory cytokine interleukin-6 were reduced by 2-fold ($p<0.001$) in the Two Dose MP group, consistent with the anti-inflammatory effects of preoperative MP administration. However, the incidence of low cardiac output syndrome was 46% (17/37) in the Single Dose and 38% (15/39) in the Two Dose MP groups ($p=0.51$). Two

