The present study will examine a cassette of MMP types corresponding to three important soluble MMP classes: the interstitial collagenases (MMP-1,-8,-13), gelatinases (MMP-2,-9) and matrilysin/stromelysin (MMP-3,) using a multiplexer approach which has been optimized, validated and calibrated for each of these MMP species. As published reports describe an apparent cell and stimulus-specific effect of PGE1 on production of MMPs¹⁰³, the net effect of PGE1 administration as a confounding variable on total circulating MMP levels in neonates pre- and post-CPB is difficult to predict. It is likely that the effects on augmentation or suppression of individual MMPs in this setting will be tissue specific. Our study will provide the initial clinical data for further investigation of this topic.

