Multiple correlation analyses will be performed between the inflammatory markers and other continuous outcome measures, such as fluid balance, inotropic score and hemodynamic variables. An assessment will also be made of the association between the inflammatory markers and categorical variables, such as the composite morbidity-mortality outcome and its components. Analyzed safety variables will include all reported adverse events, the incidence of acute renal injury and postoperative creatinine, hyperglycemia and infection.

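### The marker-outcome correlations specify no adjustment for randomised arm or surgery type, so pooled associations can reflect drug effect or case mix

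*Combined protocol and SAP*

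**What the plan says.** Section 12.4 states "Multiple correlation analyses will be performed between the inflammatory markers and other continuous outcome measures, such as fluid balance, inotropic score and hemodynamic variables", and section 12.10 has the same sentence. For categorical outcomes, section 12.10 (and 12.4 in the same words) adds "An assessment will also be made of the association between the inflammatory markers and categorical variables, such as the composite morbidity-mortality outcome and its components". Neither section names treatment arm, surgery type, any other covariate, a correlation method or a marker time point for these analyses.

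Covariate adjustment is written for a different analysis: "The primary analysis will be adjusted for underlying diagnosis and surgeon". A general clause in both sections promises multivariable handling of significant baseline imbalances between the arms.

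Other parts of the protocol bear on the point:
- Section 1.2 hypothesises that MP improves the clinical course. Section 2.2 hypothesises that it alters cytokine production and other biomarkers.
- Section 7.1.3 says of surgery type (corrective or palliative) and surgeon that they "are potential prognostic factors that may affect the primary outcome".
- Section 1.3.1.4 speaks of "the net effect of PGE1 administration as a confounding variable on total circulating MMP levels" as hard to predict.
- Section 7.1.6 and Appendix 2 give one sample before study drug and four after it, for 18 markers.
- Section 4 sets a two-sided 0.05 level for all endpoints with no multiplicity adjustment.
- Section 12.11 refers to a subsequent SAP. No separate text of it is in the documents.

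**The concern.** The plan's hypotheses place MP on both sides of each post-drug correlation. If MP lowers a marker and also moves the outcome, the two arms form two displaced clouds of points. A correlation over all infants then picks up the displacement, even if marker and outcome are unrelated inside each arm. Surgery type does the same wherever palliative and corrective cases differ in both marker and outcome, and this includes the pre-drug sample.

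The general imbalance clause does not close the gap. It concerns baseline differences between arms, so it cannot supply an arm term. Surgery type is a stratification factor and is unlikely to trigger it.

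At stake is the interpretation of the marker results. A marker that mainly indicates who received MP, or who had a palliative operation, could be reported as related to fluid balance, inotropic score or the composite. With 18 × 4 = 72 post-drug marker-time pairs per outcome (90 with the pre-drug sample), many tests are exposed.

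**Working it through.** **Inputs.** From sections 12.2 and 12.8: inotropic score SDs 3.6 and 3.9, means 14.4 and 15.0 in the earlier trial, a difference of 2 to be detected, 95 per arm. From section 4: 1:1 allocation and a two-sided 0.05 level. The documents do not give the size of the marker shift, the palliative share or the surgery-type shifts. These are assumed and shown as ranges.

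**Step 1: the plan's own figure.** Pooled SD = √((3.6² + 3.9²)/2) = 3.753. Standard error = 3.753 × √(2/95) = 0.545. Power = Φ(2/0.545 − 1.96) = 95.7% (95.5% by t-test). The stated power above 95% is reproduced. In SD units the difference is 2/3.753 = 0.533. The difference seen in the earlier trial is 0.6/3.753 = 0.16.

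**Step 2: correlation created by pooling arms.** Take zero correlation within arm, and arm shifts dM (marker) and dY (outcome) in SD units:

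r = (dM·dY/4) / √[(1 + dM²/4)(1 + dY²/4)]

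Example with dM = 1 and dY = 0.533: r = 0.133/√(1.25 × 1.071) = 0.115.

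**Step 3: rejection rate at n=190.** The test statistic is centred at atanh(r) × √187, and |r| of about 0.142 is significant. For the example, 0.1156 × 13.67 = 1.58, and the rejection rate is 1 − Φ(1.96 − 1.58) = 35%.

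| Outcome shift (SD) | Assumed marker shift (SD) | Pooled r | Tests significant |
|---|---|---|---|
| 0.533 | 0.5 | 0.06 | 14% |
| 0.533 | 1.0 | 0.12 | 35% |
| 0.533 | 1.5 | 0.15 | 57% |
| 0.25 | 1.0 | 0.055 | 12% |
| 0.16 | 1.0 | 0.036 | 8% |
| 0 | any | 0 | 5% |

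A simulation of 4,000 runs gives 14%, 36% and 56% for the first three rows. Partial correlation adjusted for arm brings these to 4.8% to 5.0%.

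**Step 4: surgery type alone.** The same formula applies with q(1−q) in place of 1/4, where q is the palliative share. With q of 30% to 50% and equal shifts in marker and outcome:
- 0.3 SD: r about 0.02, 6% significant.
- 0.5 SD: r 0.05 to 0.06, 11% to 13%.
- 0.8 SD: r 0.12 to 0.14, 37% to 48%.

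**Step 5: distortion of a real association.** Add a within-arm correlation of 0.20 to the numerator in Step 2, with dY = 0.533 and dM = 1. The pooled r is 0.29 if both shifts go the same way and 0.06 if they oppose. Pooling can hide an association as well as create one.

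**The case against.** Several points on the other side have weight.

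**Silence is not a decision.** A reader might infer that the plan has chosen to run unadjusted correlations. It has not said so: the phrase about multiple correlation is ambiguous and a later SAP is announced. What stands is that no adjustment is specified.

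**An MP effect on the markers is a hypothesis.** A reader might take the earlier trial as proof, since section 1.3.1 reports that levels of "interleukin-6 were reduced by 2-fold". Those were preoperative levels after an extra preoperative dose, two doses against one. This is neither a placebo comparison nor a post-bypass measurement.

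**The arm artefact needs both shifts.** Section 1.3.1 reports that the marker gain was not matched by better clinical outcomes and that inotropic requirement did not differ. With no outcome shift the artefact is zero. However, the same section reports higher creatinine (p=0.03) and poorer diuresis (p=0.05) with two doses, and an adverse shift creates correlation just as a beneficial one does. Fluid balance is one of the outcomes named in 12.4.

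**The 0.53 SD shift is a powered difference, not an expected one.** This is correct, so the 14% to 57% range is not a forecast.

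**Purpose.** A reader might infer that these correlations are meant to establish predictors or mediators. The remark in section 1.3.1 about biomarkers for predicting the postoperative course describes the group's earlier work, and no mediation analysis is planned. If pure prediction in the mixed population were the aim, a pooled association would be a real one. The plan states neither aim, which is a reason to specify the analysis.

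**Conclusion.** The concern holds as an under-specification with a better method at hand. Sections 12.4 and 12.10 give no arm or surgery-type term for the marker-outcome analyses, and the plan's own hypotheses and prognostic factors make pooled associations hard to interpret.

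The size is conditional. It assumes complete marker data on 190 infants, normal variables, no within-group correlation, and shifts the documents do not supply. Under those assumptions the false-positive rate runs from 5% (MP does not move the outcome) through about 8% (0.16 SD outcome shift, 1 SD marker shift) to 57% (0.53 SD and 1.5 SD). Surgery type alone contributes about 11% to 48% at 0.5 to 0.8 SD. No single figure should be read as the expected error.

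The calculation covers continuous outcomes only, so nothing here quantifies the composite or its components. The pre-drug sample cannot carry bias from study MP, though surgery type can still confound it. The primary comparison, the randomised comparison of markers between arms and the safety analyses are not affected.

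**What to change.** In sections 12.4 and 12.10, replace the pooled correlations with partial correlation or regression of outcome on marker, and use logistic regression for categorical outcomes. Specify:
- adjustment for randomised arm and for corrective versus palliative surgery;
- the infant's baseline marker value as a further covariate for post-drug samples;
- surgery type as the only required adjustment for pre-drug samples;
- examination of marker-by-arm interaction before a common association is reported;
- the marker time points and the correlation method.

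Preoperative PGE1 exposure, if existing records hold it, and bypass duration belong in sensitivity analyses at most. PGE1 is not a named item in Table 2. Bypass duration arises after study drug, which section 8 places before skin incision, so it should not be a routine covariate.

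The cost is revised wording and a few degrees of freedom. Arm, surgery type and the baseline sample are already held, so no new procedure or sample is needed.
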